6.3 Drug Accountability

The Investigator and investigational site staff are responsible for maintaining an accurate inventory and accounting of MM-398. A record of all vials of study drug received and administered will be maintained on an investigational drug inventory form provided by the Sponsor. The following information will be recorded:

- Date and quantity of study drug received
- Date and quantity of study drug dispensed from the pharmacy per patient
- Date and quantity of study drug administered to each patient
- Date and quantity of study drug destroyed (if prepared and dispensed, but not administered for any reason, the study drug may not be returned to inventory)
- Date and quantity of study drug returned to sponsor

Each shipment of study drug will contain an invoice describing the amount of drug shipped to the investigational site. The information on the invoice will be verified against the actual amount of drug received, after which the Investigator or the Investigator's designee will place the invoice in the Investigator's file.

At each monitoring visit, the Sponsor's monitor will reconcile the information on the investigational drug inventory form with the actual amount of study drug remaining at each site. At the conclusion of the study, the monitor will package and ship all unused vials of study drug back to Sponsor for destruction. Following use, empty vials of study drug may be destroyed according to local regulatory and environmental requirements. A record of any such destruction will be placed in the Investigator's file.

6.4 Concomitant Therapy

All concurrent medical conditions and complications of the underlying malignancy will be treated at the discretion of the Investigator according to acceptable local standards of medical care. Patients should receive analgesics, antiemetics, antibiotics, anti-pyretics, and blood products as necessary. Glucocorticoids and anti-seizure medication is permitted for patients with brain metastases (Expansion Phase Cohort 3; see restrictions on anti-convulsants in section 6.5

below). Although warfarin-type anticoagulant therapies are permitted, careful monitoring of coagulation parameters is imperative, in order to avoid complications of any possible drug interactions. All concomitant medications, including transfusions of blood products, will be recorded on the appropriate case report form.

Guidelines for treating certain medical conditions are discussed below; however, institutional guidelines for the treatment of these conditions may also be used. The concomitant therapies that warrant special attention are discussed below.

6.4.1 Antiemetic Medications

Dexamethasone and a 5-HT3 blocker (e.g., ondansetron or granisetron) will be administered to all patients as premedications unless contraindicated for the individual patient. Antiemetics will also be prescribed as clinically indicated during the study period.

6.4.2 Granulocyte Colony Stimulating Factors

Use of granulocyte colony-stimulating factors (G-CSF) is permitted to treat patients with neutropenia or neutropenic fever; prophylactic use of G-CSF will be permitted only in those patients who have had at least one episode of grade 3 or 4 neutropenia or neutropenic fever while receiving study therapy or have had documented grade 3 or 4 neutropenia or neutropenic fever while receiving prior anti-neoplastic therapy.

6.4.3 Therapy for Diarrhea

Acute diarrhea and abdominal cramps, developing during or within 24 hours after MM-398 administration, may occur as part of a cholinergic syndrome. The syndrome will be treated with atropine. Prophylactic or therapeutic administration of atropine should be considered in patients experiencing cholinergic symptoms during the study.

Diarrhea can be debilitating and on rare occasions is potentially life-threatening. Diarrhea should be managed according to institutional guidelines, or according to the guidelines developed by an ASCO panel for treating chemotherapy-induced diarrhea, abstracted below [23].

Clinical Presentation	Intervention
Diarrhea, any grade	Oral loperamide (2 mg every 2 hours for irinotecan induced
Diamica, any grade	diarrhea): continue until diarrhea-free for ≥ 12 hours
Diarrhea persists on loperamide for	Oral fluoroquinolone x 7 days
> 24 hours	of al hubbolumoione x / days
Diarrhea persists on loperamide for	Stop loperamide; hospitalize patient; administer IV fluids
>48 hours	Stop toperannue, nospitalize patient, administer IV nulus
ANC < 500 cells/ μ L, regardless of	Oral fluoroquinolone (continue until resolution of neutropenia)
fever or diarrhea	oral nuoroquinoione (continue until resolution of neutropenia)
Fever with persistent diarrhea, even	Oral fluoroquinolone (continue until resolution of fever and
in the absence of neutropenia	diarrhea)

Table 11: Recommendations for Management of Chemotherapy Induced Diarrhea

6.5 **Prohibited Therapy**

The following drugs are noted in the irinotecan prescribing information as interacting with irinotecan: St. John's Wort, CYP3A4 inducing anticonvulsants (phenytoin, phenobarbital, and carbamazepine), ketoconazole, itraconazole, troleandomycin, erythromycin, diltiazem and

verapamil. Treatment with these agents and any other that interact with irinotecan, should be avoided wherever possible.

Thus, the following therapies are not permitted during the trial:

- Other anti-neoplastic therapy, including cytotoxics, targeted agents, endocrine therapy or other antibodies
- Potentially curative radiotherapy; palliative radiotherapy is permitted
- Any other investigational therapy is not permitted

7 Study Procedures

7.1 Clinical Procedures

7.1.1 Medical History

Medical history will include all pertinent prior medical conditions, surgeries or other medical procedures.

7.1.2 Physical Examination

Physical examination will include a careful assessment of all body systems, including the skin; central and peripheral nervous system; eyes, ears, nose and throat; respiratory and cardiovascular systems; abdomen and extremities. Particular attention should be made to areas of possible neoplastic involvement.

7.1.3 Vital Signs

Vital signs will include weight, resting blood pressure, pulse, respiratory rate and temperature.

7.1.4 ECOG Performance Score

The Eastern cooperative oncology group (ECOG) Performance Score will be obtained by the PI or his/her designee by questioning the patient about their functional capabilities.

7.1.5 ECG

A 12 lead ECG will include a description of the cardiac rate, rhythm, interval durations and an overall impression.

7.1.6 Disease Evaluation

Tumor response will be evaluated according to the Response Evaluation Criteria in Solid Tumors (RECIST) version 1.1 or modified RECIST criteria (for CNS disease only; Cohort 3), to establish disease progression by computed tomography (CT) or MRI. At baseline, all Expansion Phase patients with extracranial disease will also have a standard fluorodeoxyglucose (¹⁸F-FDG) positron emission tomography (PET)/CT scan in order to identify lesions that are metabolically active; follow-up PET/CT scans are not required. In addition, other radiographic or scintigraphic procedures (such as radionuclide bone scans), as deemed appropriate by the Investigator, will be performed to assess sites of neoplastic involvement. The same method of assessment must be used throughout the study. Patients in Cohort 3 with both CNS and non-CNS disease will have separate evaluations of each disease type. Investigators should select target and non-target lesions in accordance with RECIST v1.1 guidelines, or modified RECIST criteria as specified below for brain lesions. Follow up measurements and overall response should also be in accordance with these guidelines, unless otherwise specified below (Cohort 3 only).

7.1.6.1 Modified RECIST Criteria for Cohort 3

Tumor response for CNS disease will be evaluated according to modified RECIST criteria as described previously [37], and as specified below. A maximum of five target lesions (\geq 5 mm in size of long axis, with at least one lesion measuring \geq 1 cm) will be identified at baseline, with the remaining lesions followed as non-target lesions. Selection of necrotic or cystic lesions as target lesions should be avoided if other solid lesions are present. All target lesions should be measured for each follow-up disease evaluation, even if lesion size decreases to < 5 mm. If a lesion is too small to measure, a default value of 3 mm should be used. Table 12 describes the definition of response for CNS disease only; non-CNS disease will be assessed separately according to RECIST v1.1.

Response	Definition
Complete Response (CR)	Disappearance of all target and non-target lesions; or lesions do not show
	any gadolinium enhancement and are completely necrotic
Partial Response (PR)	\geq 30% decrease in the sum longest dimension (LD) of target lesions
	(taking as reference
	the baseline sum diameters) and an absolute decrease of at least 5 mm in at
	least one target lesion; non-target lesions do not meet the criteria for PD
Stable Disease (SD)	Neither sufficient shrinkage to qualify for PR nor sufficient increase to
	qualify for PD, taking as reference the smallest sum diameters while on
	study; non-target lesions do not meet the criteria for PD
Progressive Disease (PD)	\geq 20% increase in the sum LD of target lesions (taking as reference the
	smallest sum on study, including the baseline sum if that is the smallest on
	study) and an absolute increase in size of at least 5 mm in at least one
	target lesion, or the appearance of one or more new lesions of at least 6
	mm in size; and/or growth of non-target lesion(s) sufficient to determine
	unequivocal progression

 Table 12: CNS Response Assessment for Cohort 3

7.1.6.2 Criteria for Treatment Termination due to Progressive Disease

Pilot Phase and Expansion Phase patients in Cohorts 1 and 2 will be discontinued from study treatment due to progressive neoplastic disease, assessed by RECIST v1.1 as described in section 7.1.6 above. Patients in Expansion Phase Cohort 3 will have CNS and non-CNS disease assessed separately. Patients in Cohort 3 should be discontinued from study treatment for radiographic evidence of progressive disease (PD) in the CNS (see Table 12), however, patients may stay on study treatment at the Investigator's discretion for the following reasons:

- Radiographic evidence of non-CNS PD only (no evidence of CNS PD)
- Symptomatic progression of CNS disease (without radiographic evidence of PD)

If there is evidence that a patient in Expansion Phase Cohort 1 or Cohort 2 experiences PD yet has also derived clear clinical benefit from study treatment, then the Investigator, Medical Monitor and Sponsor may review the specifics of the case at the request of the Investigator. Such a patient may remain on study if the consensus judgment is that continued treatment is in the patient's best interest.

7.2 Laboratory Procedures

7.2.1 Complete Blood Count

A complete blood count will include a white blood count (WBC) and differential, hemoglobin, hematocrit and platelet count.

7.2.2 Serum Chemistry

Serum chemistry will include electrolytes (sodium, potassium, chloride and bicarbonate), BUN, serum creatinine, glucose, bilirubin, AST, ALT, alkaline phosphatase, lactate dehydrogenase, uric acid, total protein, albumin, calcium, magnesium and phosphate. Iron levels (ferritin, iron and transferrin saturation) will be measured at the screening visit, at the time of the first MM-398 dose of Cycle 2 (first additional cycle) and at the 30 Day Follow-up visit.

7.2.3 Biomarker Samples

Whole blood and plasma will be collected to potentially identify factors that may correlate with tumor response, sensitivity or resistance to MM-398, and MM-398 PK. Examples of potential analyses include cytokine levels (e.g. MCSF1, and IL-6), growth factors (e.g. IGF1 and EGFR family receptors and ligands), enzyme levels (e.g. MMP9).

7.2.4 Coagulation Profile

A coagulation profile will include a partial thromboplastin time and an international normalized ratio.

7.2.5 UGT1A1*28

A whole blood sample will be collected from all patients at baseline to test for UGT1A1*28 allele status. The result is not needed prior to the initial dose of MM-398. Both the starting dose and dose modifications for toxicities will be the same for all patients regardless of UGT1A1*28 genotype, as described in section 6.1.6.3.

7.2.6 Urinalysis

A urinalysis will include descriptions of color and clarity; pH; specific gravity; and analyses of blood, glucose, ketones and total protein. A microscopic examination of the urine, to include WBC, RBC, bacteria and casts will be performed if the urinalysis is abnormal.

7.2.7 Urine or Serum Pregnancy Test

A urine or serum pregnancy test will be obtained for all females of childbearing potential. Exempt female patients will include those who have undergone a bilateral oophorectomy or hysterectomy or who are menopausal (defined as absence of a menstrual cycle for at least 12 consecutive months).

7.2.8 Pharmacokinetic Assessments

Plasma samples will be collected to determine the levels of MM-398 and SN-38. Additional analytes which may impact the pharmacokinetics of MM-398 may also be measured from this sample. Directions for processing and shipping the PK plasma samples can be found in the study manual. The PK time points outlined in Table 13 below will be drawn during Cycles 1-3.

Sample	Time-point (Cycles 1-3)	Window
1	Immediately prior to MM-398 infusion on Day 1	-5 mins
2	At the end of the MM-398 infusion	+5 mins
3	+2 hours after the completion of the MM-398 infusion	±30 mins
4	+ 48 hours after the completion of the MM-398 infusion	±24 hours
5	+168 hours/7 days after the completion of the MM-398 infusion	±24 hours
6	Immediately prior to MM-398 infusion on D15	-24 hours
7	30 day follow up visit	

 Table 13: Summary of PK Timepoints in Treatment and Follow-up Phases

7.3 Tissue Collection

7.3.1 Fresh Tumor Biopsies

7.3.1.1 Pilot Phase Biopsies

Two biopsies will be collected on Day 4 of the ferumoxytol phase and two biopsies will be collected three days after the first dose of MM-398.

On Day 4 of the ferumoxytol phase, the lesion(s) selected for biopsy will be based on the results of the FMX-MRI obtained on Days 1, 2 and 4. The first core biopsy will be in the region of the tumor that shows the greatest signal change based on FMX-MRI and the second core biopsy will be taken from the region that shows the least signal change based on FMX-MRI.

On Cycle 1 Day 4 of the MM-398 Treatment phase, the lesion(s) selected for biopsy will be based on the results of the FMX-MRI obtained on Days 1, 2 and 4 of the ferumoxytol phase. The post-treatment biopsies will be collected from a previously non-biopsied lesion. The first core biopsy will be in the region of the tumor that shows the greatest signal change on either the T2* or T1 sequences, based on FMX-MRI. The second core biopsy will be taken from the region that shows the least signal change based on FMX-MRI, avoiding obvious areas of necrosis.

7.3.1.2 Expansion Phase Biopsies

A Post-treatment core biopsy must be collected at 72 h (+/- 1 day) after the C1D1 administration of MM-398. Any lesion that is amenable to a safe multi-pass core biopsy procedure may be selected. Expansion Phase patients in Cohort 3 with central nervous system (CNS) disease only are not required to undergo biopsy; however patients in Cohort 3 with non-CNS disease will be required to submit a biopsy sample, if a core biopsy can be safely obtained from a site of extracranial disease. Three passes should be obtained with the first two passes snap frozen and the third pass, if available, formalin fixed; See Laboratory Manual for details on processing and handling of the biopsy samples. Frozen samples will be used to measure tumor drug (CPT-11) and metabolite (SN-38) levels in order to further establish the mechanism of action of MM-398 and evaluate the relationship with tumor ferumoxytol levels as measured by FMX-MRI. Formalin fixed samples may be used to explore potential markers of sensitivity and resistance to irinotecan other pharmacodynamic markers related to activity of MM-398.

7.3.2 Archived Tumor Samples

Archived tumor blocks or unstained FFPE slides containing tumor tissue, prepared at the time of initial diagnosis and at the time of metastasis (if available) will be collected from each patient. Archived paraffin blocks may be used if available and will be returned to the site upon sectioning by sponsor or sponsor designated central lab. Samples will be used to explore potential markers

of sensitivity and resistance to irinotecan, including but not limited to the following: DNA damage repair pathways (e.g. Topo1, BRCA1/2, and SLFN11), growth factor pathways (IGF1 and EGFR family receptors and ligands), and factors involved in CPT-11 conversion to SN-38 (e.g. macrophage content and CES activity).

7.4 Ferumoxytol Magnetic Resonance Imaging

It is anticipated that the MRI parameters will need to be optimized in patients that are enrolled at the beginning of the study and/or in the Expansion Phase, in order to assess any correlations between FMX-MRI signal and TAMs, pharmacodynamic markers, or tumor response. A detailed FMX-MRI protocol is included in the study imaging manual, but briefly, each patient will be required to undergo their FMX-MRIs on the same scanner to reduce inter-scan variability. Each MRI study will be evaluated for image quality and signal characteristics of tumors and reference tissue on T1-, T2- and T2*- weighted sequences. Once a completed set of images from each patient has been received, the images will be loaded onto the viewing workstation for qualitative review and then sent to a quantitative lab for analysis.

During the Expansion Phase, multiple MR images will be collected on Day 1-Day 2 of the ferumoxytol period, at various time points depending on the scan group to which the patient is assigned. The body areas to be scanned will be determined by the location of the patient's disease; detailed instructions are described in the study imaging manual. All patients will have a baseline image acquired prior to the ferumoxytol infusion, and either a second successive image (baseline repeat; Scan Group 1) or a second image occurring 1-4 h after the end of ferumoxytol administration (Scan Groups 2 and 3). All patients will return on Day 2 for a 24 hour (16-24 h window) FMX-MRI using the same protocol and sequences as on Day 1. Patients enrolled into Scan Groups 1 and 2 will require one additional scan either at 24 h or 2 weeks, for a total of 4 scans. Patients will be assigned in an alternating fashion to Scan Groups 1 and 2 before enrollment into Scan Group 3 begins. See Table 14 below for additional details on scan groups and required time points.

Scan Group	N ^a	Baseline	Baseline (repeat)	1-4 h	24 h (16-24 h)	24 h (repeat)	2 wk (+/- 1 Day) Baseline
1	5	Х	Х		Х		Х
2	5	Х		Х	Х	Х	
3	10	Х		Х	Х		

Table 14: Summary of Expansion Phase MRI Scan Groups (Cohorts 1 and 2)

^a Enrollment into Scan Groups 1 and 2 may be increased at the discretion of the Sponsor, in the event that any of the images are not evaluable, or it is determined that more information is needed from the additional scan time points. In this case, enrollment into Scan Group 3 will be decreased by a corresponding number of patients.

Table 15: Expansion Phase Cohort 3 MRI Scan Time Points

Scan Group	Ν	Baseline	Baseline (repeat)	1-4 h	24 h (16-24 h)	24 h (repeat)	2 wk (+/- 1 Day) Baseline
4 (cohort 3)	10	Xa		X ^b	Xª		

^a Patients with extra-cranial disease will have MRIs of two body areas at baseline and 24 h: one brain scan and one body scan (body scan will capture the majority of the patient's extra-cranial disease; see imaging manual for details)

^b Brain scan only will be completed at this time point

8 Schedule of Assessments

8.1 Pilot Phase (Closed)

PILOT PHASE SCHEDULE OF ASSESSMENTS REMOVED (MM-398-01-01-02 Version 3.0). This portion of the trial has been completed and the schedule of assessments has been removed from this version of the protocol to reduce confusion during operation of Expansion phase.

Ð	
0	
GR	
IPSEN	

Expansion Phase 8.2

	Screening Period	Ferumoxytol (FMX)Period	oxytol Period				MM-398	MM-398 Treatment Period	nt Period		Follow Up Period
Procedure	-28d	Day 1	Day 2	5	ycle 1 ²³	Cycle 1 ²³ , 2, and 3	d 3	Additional Cycles (every 1 month) ²⁸	al Cycles month) ²⁸	Every 8w	+30d ²²
		•		D1	D3	D8	D15	D1	D15	arter 1 ²² dose	
Informed consent	\mathbf{X}^1										
Medical history	\mathbf{X}^1										
Demographics	\mathbf{X}^{1}										
Physical exam	\mathbf{X}^2			Х				Х			X
Vital signs	X^2	X^3		Х		Х	Х	Х	Х		Х
ECOG PS	\mathbf{X}^2			Х				Х			Х
CBC	\mathbf{X}^2			Х		Х	Х	Х	Х		Х
Serum chemistry ²¹	$X^{2,16}$			Х		Х	Х	X^{16}	Х		X^{16}
UGT1A1*28	$X^{1,17}$										
Coagulation profile ²¹	\mathbf{X}^2			Х				Х			Х
Urinalysis	\mathbf{X}^2										Х
Pregnancy test	\mathbf{X}^2										Х
ECG	$\mathbf{X}^{1,4}$										X^4
FMX-MRI		ςX	X^{6}				\mathbf{X}^7				
Ferumoxytol infusion		X^{25}									
Tumor biopsy ⁸					X^9						
Archived tissue ¹⁰	Х										
Plasma for PK				X^{11}	X^{12}	X^{13}	X^{14}				Х
Biomarker analysis ^{18,21}				X^{14}				Х			Х
Concomitant meds	\mathbf{X}^{1}	Х	Х	Х		Х	Х	Х	Х		Х
MM-398 dosing ¹⁵				Х			Х	Х	Х		
AE reporting						Contin	uous Mc	Continuous Monitoring			
Disease evaluation	$X^{1,24}$									X^{20}	${ m X}^{19}$
¹ Procedures to be completed within 28 days of ferumoxytol dose	1 within 28 days	of ferumox;	ytol dose								

² Procedures to be completed within 7 days of ferumoxytol dose

³ Body weight to be collected within 7 days of ferumoxytol dose

⁴ Two independent readings at least 1 minute apart ⁵ Procedure completed at Cycle 2 only

 6 One reading prior to the start of the MM-398 infusion and one reading post infusion of MM-398 is required 7 Two FMX-MRI collected as outlined in section 7.4 and Table 14 and Table 15

 8 One MRI at 24 h (16-24 hour window) except Scan Group 2, who will undergo 2 repeat scans at the 24 h timepoint 9 For Scan Group 1 only, one MRI scan will be performed during Cycle 1 only (±1 day)

Page 57 of 74

- ¹⁰ Biopsy required for Cohorts 1 and 2, as well as Cohort 3 patients with extracranial disease that can be safely biopsied
 - ¹¹ Post-Treatment Biopsy collected 72h post C1D1 MM-398 infusion
- ¹² Collection of archived tumor block or paraffin embedded slides, if available
- ¹³ Samples collected at the following timepoints on C1D1 of the MM-398 Treatment Phase: just prior to the MM-398 infusion (-5 mins); at the end of the MM-398 infusion (± 5 mins); ± 2 hours after the completion of the MM-398 infusion (± 30 mins);
 - ¹⁴ Sample collected +48 hours after the completion of the MM-398 infusion (± 24 hours)
- ¹⁵ Sample collected +168 hours/7 days after the completion of the MM-398 infusion (± 24 hours)
 - ¹⁶ Sample obtained just prior to dosing with MM-398 (-24 hour window)
- ¹⁷ MM-398 administration should occur ± 2 days from scheduled date of administration
- ¹⁸ In addition to normal labs, iron levels will be measured at the screening visit, at the time of the first MM-398 dose of Cycle 2 (first additional cycle) and at the 30 Day Follow-up visit.
- ¹⁹ Result not required prior to enrollment in the study., but patients positive for UGT1A1*28 Both the starting dose and dose modifications for toxicities will be the same for all patients regardless of UGT1A1*28 genotype, may have future doses reduced as described in section 6.1.6.3
 - ²⁰ Blood will be collected for biomarker analyses
 - ²¹ Unless completed in the prior 6 weeks
- ²² Disease evaluations should be done every 8 weeks (\pm 7 days) after 1st dose
- 23 Visit for samples should be obtained $\pm\,2$ days from scheduled date of collection
 - 24 The 30-Day Follow-Up visit should occur 30 days (± 7 days) after last dose
- ²⁵ The Cycle 1 Day 1 visit should occur within 7 days of ferumoxytol infusion
- ²⁶ In addition to contrast-enhanced CT and/or MRI, ¹⁸F-FDG PET/CT scan required at baseline only (patients with extracranial disease only)
- reactions, including monitoring blood pressure and pulse during administration and for at least 30 minutes following the infusion as per the ferumoxytol ²⁷ Administer while patient is in a reclined or semi-reclined position. Patients should be closely monitored for signs and symptoms of serious allergic label instructions. Ferumoxytol administration outlined in section 6.2.3

9 Adverse Event Reporting

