4.2 Study Stages and Treatment Design

There are four stages to this study, defined as periods:

- Screening Period (-28d): patients undergo screening assessments to determine if they are eligible for the study
- Ferumoxytol (FMX) Period (Day 1 Day 2): patients receive ferumoxytol (FMX) infusion and undergo required FMX-MRI scans prior to receiving MM-398.
- MM-398 Treatment Period (C1D1 progression of disease): patients receive an MM-398 dose of 60 mg/m² every 2 weeks, which should be dose escalated to 80 mg/m² every 2 weeks in subsequent doses depending on patient tolerance, other required assessments, and undergo a post-treatment (MM-398) multiple pass core biopsy

• Follow Up Period (+30d from last dose): patients return to clinic 30 days following the last dose of MM-398 for final safety assessments

For all enrolled patients, a single dose of 5 mg/kg of ferumoxytol will be administered at Day 1 during the ferumoxytol period by intravenous infusion in 50-200 mL of 0.9% sodium chloride or 5% dextrose over a minimum period of 15 minutes following dilution. The total single dose will not exceed 510mg, the maximum approved single dose of ferumoxytol.

MM-398 will be administered by intravenous (IV) infusion over 90 minutes at a dose of 60 mg/m² every two weeks. The MM-398 period (C1D1) should begin within 7 days of the ferumoxytol infusion. The dose of MM-398 should be escalated to 80 mg/m² every two weeks depending on patient tolerance.

All patients will be treated until disease progression (see section 7.1.6.2) or unacceptable toxicity.

Enrollment and Treatment

Between 12 and 20 patients will be enrolled in this the Pilot Phase of the study. The Expansion Phase will enroll up to 30 evaluable patients, in three cohorts. The total enrollment for the study will be approximately 45 patients.

Patients receiving ferumoxytol and not completing all assessments and/or those who do not have evaluable FMX MR images, may still proceed to the MM-398 treatment phase; however additional patients may be enrolled to ensure that adequate MRI data are collected to achieve the objectives of the study. In addition, in order to be considered evaluable from a pharmacodynamic standpoint for the Expansion Phase, patients must have received MM-398 and completed at least one CT scan at the 8-week post-treatment time point.

5 Patient Selection and Discontinuation

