11.3.2.1 Progression-Free Survival (PFS)

PFS is defined as the time in months from first dose of MM-398 to the date of radiologic disease progression by RECIST or mRECIST (cohort 3 CNS disease) per Investigator assessment or death due to any cause, whichever occurs first.

Date of Progression: the earliest date that an overall tumor response of PD or death is recorded. Data handling conventions for determining the date of progression are outlined in [Table 3](#).

If progression is associated with a new lesion, the date of progression is the date when the new lesion was detected, where progression is associated with the sum of target lesions and different lesions are measured on different dates in a given visit, use the earliest date for visit as the date of progression.

For patients who do not have qualifying progressive disease or death, the date of censoring for PFS is the date when the last valid tumor assessment determined a lack of progression. If the last valid tumor assessment involves measurements over multiple days in a visit, the date of the last measurement will be the censoring date. A tumor assessment is considered valid if data has been recorded for all target lesions and absence of new lesions is documented. Date of last non-PD/non-NE assessment is the date of first dose date for patients without a valid post-baseline tumor assessment.

Table 3 Data handling rules for PFS analysis

Condition	Date of Progression or Censoring	Event
No baseline tumor assessments	Date of first dose of MM-398	Censored
Progression documented within 12 weeks* of baseline or the last non-PD/non-NE tumor assessment	Earliest of: 
 • date of radiographic assessment showing new lesion (if progression based on new lesion) or • date of radiographic assessment of target/non-target lesions in which progression is documented 	Progression
Death within 12 weeks* of last non-PD tumor assessment without documented progression	Date of death	Progression
Death or first documented progression after 12 weeks* from last non-PD tumor assessment	Date of last non-PD assessment	Censored
None of the following: 
 • documented progression • death • treatment termination • New anticancer therapy started • cancer-related surgery 	Date of last non-PD assessment	Censored

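### SAP Table 3 starts its 12-week PFS limit at the baseline scan, so some progressions at an on-schedule first scan are censored before PFS begins

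*Protocol*

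**What the plan says.** **Timing of scans (Protocol).** In the Section 8.2 schedule the screening disease evaluation carries footnote 1: "Procedures to be completed within 28 days of ferumoxytol dose". Another footnote to that schedule adds: "The Cycle 1 Day 1 visit should occur within 7 days of ferumoxytol infusion". Section 4.2 repeats the 7-day limit: "The MM-398 period (C1D1) should begin within 7 days of the ferumoxytol infusion". For follow-up the footnotes say "Disease evaluations should be done every 8 weeks", with 7 days allowed either side, counted from first dose.

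From about the eighth footnote on, the superscripts in the schedule and the printed footnote numbers are out of step. Footnote 1 is not affected and Section 4.2 confirms the 7 days, so nothing below depends on the numbering.

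**PFS rules (SAP 11.3.2.1).** PFS runs from the first dose of MM-398. Table 3 treats as an event: "Progression documented within 12 weeks* of baseline or the last non-PD/non-NE tumor assessment". It censors, at the date of the last non-PD assessment: "Death or first documented progression after 12 weeks* from last non-PD tumor assessment". The asterisk gives 16 weeks for a sensitivity analysis. The text before the table adds: "Date of last non-PD/non-NE assessment is the date of first dose date for patients without a valid post-baseline tumor assessment". It defines a valid assessment as one with all target lesions recorded and new lesions documented as absent.

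**The concern.** The baseline window is counted back from ferumoxytol and the follow-up window forward from MM-398, while the 84-day limit in Table 3 spans both. A limit of this kind is meant to catch events found after missed scans. Here it can be exceeded by a patient who attended every visit in window.

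The patients exposed are those who progress at the first scan, which is the earliest point at which radiological progression can be seen on schedule. Removing some of them from the event count raises the PFS curve. Their censoring date would be the baseline scan, which lies before the PFS start.

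**Working it through.** The documents state no figure for the baseline-to-first-scan interval, so there is none to reproduce.

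**1. Inputs**
- Baseline scan: 0 to 28 days before ferumoxytol (Protocol 8.2, footnote 1).
- Ferumoxytol to first MM-398 dose: up to 7 days (Protocol 8.2 and 4.2).
- First follow-up scan: 56 days, 7 either side, after first dose, so day 49 to 63 (Protocol 8.2).
- Limit: 12 × 7 = 84 days in the main analysis, 16 × 7 = 112 days in the sensitivity analysis (SAP Table 3).

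**2. Longest intervals with every window kept**

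Baseline to first dose: 28 + 7 = 35 days. Days from baseline to first scan:

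| Baseline before first dose | Scan on day 49 | Scan on day 56 | Scan on day 63 |
|---|---|---|---|
| 21 days | 70 | 77 | 84 |
| 22 days | 71 | 78 | **85** |
| 28 days | 77 | 84 | **91** |
| 29 days | 78 | **85** | **92** |
| 35 days | 84 | **91** | **98** |

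Bold entries exceed 84 days; none exceeds 112. Consecutive later scans are at most 56 + 14 = 70 days apart, so only the first scan is exposed.

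**3. Which first-scan progressions are lost**
- *Target-lesion growth, all target lesions recorded, no new lesion.* By the SAP's definition this is a valid post-baseline assessment, so the first-dose sentence does not apply. The last non-PD assessment is the baseline scan. At 85 to 98 days the event is censored there.
- *New lesion present.* The absence of new lesions is not documented, so the assessment is not valid and the first-dose sentence applies. The interval is at most 63 days and the event counts.

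Two patients who progress equally early are thus handled in opposite ways because of lesion type.

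**4. Censoring date**

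The formula in SAP 7.6.4.1 is (date2 − date1 + 1)/(365.25/12). With baseline 35 days before first dose this gives (−35 + 1)/30.4375 = −1.1 months, a negative PFS time.

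**5. Share of first scans beyond 84 days**

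Assumption: the permitted days are independent and equally likely, with 1 to 7 days from ferumoxytol to first dose.
- Baseline 0–28 days before ferumoxytol: 29 × 7 × 15 = 3,045 combinations, of which 476 exceed 84 days, or 15.6%.
- Same, first scan always on day 56: 28 of 203, or 13.8%.
- Baseline 14–28 days before ferumoxytol: 476 of 1,575, or 30.2%.
- Baseline 0–14 days before ferumoxytol: the maximum is 14 + 7 + 63 = 84, so 0%.

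**6. Effect on PFS after the first scan**

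Assumption: 12 of 30 patients progress at the first scan, all without new lesions, and no one else is censored before it. The correct value is 1 − 12/30 = 60%. Patients censored at or before time zero leave both the event count and the number at risk:
- 0% lost: 60%.
- 15.6% lost (12 × 0.156 = 1.87): 1 − 10.13/28.13 = 64%.
- 30% lost (3.6): 1 − 8.4/26.4 = 68%.

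**The case against.** The strongest reply is that the first-dose sentence was meant to cover these patients. It follows a passage about the last valid assessment that showed no progression. Read in that light, a patient whose only post-baseline scan shows progression has no such assessment, the clock starts at first dose, and no on-schedule first-scan event is lost. The negative PFS time also suggests that the literal result was not intended. This may well be the intention, but the SAP does not say so. Its definition of a valid assessment does not exclude a scan showing progression, and Table 3 names baseline. A programmer following the text would censor.

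Other points that stand:
- The 16-week sensitivity analysis counts every on-schedule case (98 < 112).
- BOR, ORR and CBR do not use the 12-week rule.
- The study is descriptive, and the objectives name ORR and clinical benefit rate, not PFS, as key efficacy indicators.
- The share affected may be zero if sites scan close to ferumoxytol.

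A reader might infer that the ferumoxytol anchor is the cause and that tying the scan window to Cycle 1 Day 1 would cure the problem. It would not. The anchor adds only 7 of the 35 days, and a 28-day window before first dose still reaches 28 + 63 = 91 days. With baseline 1 to 28 days before first dose, 28 of 420 combinations (6.7%) still exceed 84.

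A reader might also infer that tumour growth between baseline and first dose biases the primary analysis of FMX uptake against response. Such growth does enter the size change, as it does under any screening window. Nothing in the documents suggests that the gap differs between low- and high-uptake patients, so a bias in that relationship is not shown.

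**Conclusion.** The rule is wrong as written, with a limited effect. With every visit in window, a first scan can fall 85 to 98 days after baseline. Progression there by target-lesion growth without a new lesion is then censored in the main PFS analysis, at a date up to 35 days before PFS starts. The direction is certain: the rule can only raise PFS.

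The size is not known, because the documents do not give the timing of baseline scans. Between 0% and 30% of first scans exceed the limit under the timings tried (15.6% with equally likely days). In the assumed example, PFS after the first scan reads 60% to 68% instead of 60%. The upper end needs every baseline scan to be at least 14 days before ferumoxytol and no first-scan progression with a new lesion.

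It would go too far to say that all early progressions are lost or that the response endpoints are affected.

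**What to change.** In SAP 11.3.2.1:
- In both the progression row and the after-12-weeks censoring row of Table 3, start the limit at the first dose of MM-398 whenever there is no post-baseline non-PD assessment. The longest on-schedule interval is then 63 days, inside 84.
- State that the first-dose sentence also applies to patients whose only post-baseline assessment shows progression, with or without a new lesion.
- Set any resulting censoring date to the date of first dose, never earlier.

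Optionally, summarise days from baseline scan to first dose, so that readers can see how many patients the rule would have touched.

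The cost is a few lines of SAP text and the matching programming. No protocol amendment, additional scan or new data is needed.
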